INCB050465 is being evaluated as a monotherapy in a Phase 1/2, dose-escalation and expansion study (INCB 50465-101, NCT02018861, [Phillips et al 2016](#)). As of 01 MAR 2017, data were available for 63 subjects who received INCB050465 administered orally QD or QD for 9 weeks followed by QW. Starting in NOV 2016, subjects were switched to QW dosing if they had been on study treatment for > 9 weeks ([Ramchandren et al 2017](#)). The median duration of treatment for all subjects was 114 days (range 7-520). Nonhematological adverse events observed in \geq 20% of subjects were nausea (38%), diarrhea/colitis (35%), fatigue (29%), vomiting (27%), cough (24%), rash (22%), and dizziness (21%). New or worsening Grade \geq 3 anemia, thrombocytopenia, and neutropenia occurred in 5%, 10%, and 22% of subjects, respectively. No \geq Grade 3 nonhematological treatment-related AEs were reported in \geq 10% of subjects. Serious AEs that occurred in \geq 2 subjects included diarrhea/colitis (n = 6) and hypotension (n = 3) and ventricular tachycardia, pyrexia, pneumonia, exfoliative dermatitis, syncope, and bacteremia (n = 2 each). Twelve (19%) of the 63 subjects discontinued study treatment due to the following AEs: diarrhea (n = 2), exfoliative dermatitis (n = 2), colitis, cytomegalovirus colitis, pneumonitis, rash, psoriasis, neutropenia, pneumonia, and hypercalcemia (n = 1 each). All but 1 of these events occurred after the 9-week disease assessment. No liver function test abnormalities > Grade 1 were reported while subjects were receiving study treatment. No dose-limiting toxicities were identified, and the maximum tolerated dose was not reached.

As of 01 MAR 2017, 28 objective responses as reported by investigators were observed in 57 evaluable subjects with DLBCL, FL, HL, marginal zone lymphoma, chronic lymphocytic leukemia, and mantle cell lymphoma. These results include 8 objective responses among the 11 evaluable subjects with FL; all but 1 of the objective responses occurred by the time of the 9-week disease assessment. Among the 8 objective responses, 6 demonstrated > 75% reduction in their target lesions (see [Figure 1](#)). The longest duration of study treatment among subjects with FL was approximately 14 months, with 3 of the evaluable subjects ongoing.

Figure 1: Best Percentage Change From Baseline in Target Lesion Size in Follicular Lymphoma Subjects From Study INCB 50465-101

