#### 9.2. Adverse Events

#### 9.2.1. Adverse Event Definitions

A TEAE is any AE either reported for the first time or worsening of a pre-existing event after the first dose of study drug and within 30 days of the last administration of study drug regardless of starting new anti-lymphoma therapy. Analysis of AEs (as discussed below) will be limited to TEAEs, but data listings will include all AEs regardless of their timing in relation to study drug administration. For purposes of analysis, all AEs will be considered TEAEs unless the AE can unequivocally be defined as not treatment-emergent.

Adverse events will be tabulated by MedDRA PT and SOC. Severity of AEs will be graded using the NCI CTCAE (v4.03; NCI 2010), Grades 1 through 5. The CTCAE reporting guidelines and grading details are available on the Cancer Therapy Evaluation Program website.

The subset of AEs considered by the investigator to be related to study drug will be considered treatment-related AEs. If the investigator does not specify the relationship of the AE to study drug, the AE will be considered treatment-related. The incidence of AEs and treatment-related AEs will be tabulated. In addition, serious TEAEs will also be tabulated.

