#### 9.2.2. Adverse Events of Special Interest

The number of participants who experienced TEAEs of special interest listed below will be summarized by maximum severity.

- Colitis
- Diarrhea
- Exfoliative dermatitis
- Febrile neutropenia
- Rash
- Intestinal perforation
- Pneumonitis
- Pneumonia
- PJP infection
- CMV infection
- Herpes simplex
- Varicella zoster virus infection

The time to onset of a TEAE is defined as the interval between the date of first dose of study drug and the date of the first occurrence of a TEAE. Participants who have not experienced a TEAE at the time of analysis will be right-censored at the earlier of 30 days after the last dose date and date of last study visit through the end of safety follow-up. If participants have missing or partial last dose dates of study drug or onset date of a TEAE, the partial or missing dates will be handled using the rules explained in Section 4.1.4.

Summaries of time to onset of new or worsening Grade 3 or higher AEs will be provided using descriptive statistics and the life-table method for rash, colitis, diarrhea, febrile neutropenia, pneumonia, herpes simplex, and varicella zoster virus infection. In addition, summaries of time to onset of new or worsening AEs of any grade will be provided using descriptive statistics and the life-table method for colitis, diarrhea, exfoliative dermatitis, intestinal perforation, pneumonia, pneumonitis, PJP infection, CMV infection, herpes simplex, and varicella zoster virus infection. Kaplan-Meier plots of time to onset of new or worsening Grade 3 or higher AEs will be provided for rash, colitis, and diarrhea. In addition, Kaplan-Meier plots of time to onset of new or worsening AEs of any grade will be provided for colitis and diarrhea.

Descriptive statistics of time to onset of these TEAEs of special interest are based on all participants who have experienced a TEAE at the time of analysis. To summarize these TEAEs of special interest using the life-table method, the effective sample size is defined as the number of participants at the beginning of interval minus half the participants censored in the interval. The conditional proportion is calculated as the number of first events divided by the effective sample size in the interval.

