#### 9.3.4. Worsening Laboratory Events of Special Interest

Laboratory events of special interest are listed below.

- ALT increased
- AST increased
- Absolute neutrophil count decreased

The time to onset of a worsening laboratory event is defined as the interval between the date of first dose of study drug and the date of the first occurrence of CTC grade worse than baseline for the laboratory event. Participants who have not experienced a worsening laboratory event at the time of analysis will be right-censored at the last postbaseline study visit with nonmissing CTC grade of the laboratory event.

Time to onset of worsening Grade 3 or 4 laboratory events of special interest will be summarized using descriptive statistics and the life-table method as described in Section 9.2.2, and the Kaplan-Meier plot of time to onset of worsening Grade 3 or 4 absolute neutrophil count decreased will be provided. Laboratory events of special interest to be summarized may be adjusted based on emerging data.

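### Kaplan-Meier onset plots for selected toxicities censor death and stopping treatment, so read as the share of patients affected they run high, by an uncertain amount

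*SAP*

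**What the plan says.** SAP 9.2.2 plans two sets of onset plots (Figure 4.5.1 in Appendix A): "Kaplan-Meier plots of time to onset of new or worsening Grade 3 or higher AEs will be provided for rash, colitis, and diarrhea" and "Kaplan-Meier plots of time to onset of new or worsening AEs of any grade will be provided for colitis and diarrhea". Participants without the event are "right-censored at the earlier of 30 days after the last dose date and date of last study visit through the end of safety follow-up". Under SAP 9.2.1, a treatment-emergent event must arise or worsen "after the first dose of study drug and within 30 days of the last administration of study drug".

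SAP 9.3.4 plans one more Kaplan-Meier plot, for worsening to Grade 3 or 4 neutrophil decrease (Figure 4.6.2). Its censoring rule differs: "Participants who have not experienced a worsening laboratory event at the time of analysis will be right-censored at the last postbaseline study visit" that has a nonmissing grade. It states no 30-day limit. ALT and AST get descriptive statistics and life tables but no plot.

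The life tables cover a longer list of events. For them, "the effective sample size is defined as the number of participants at the beginning of interval minus half the participants censored in the interval", and the quantity defined is the conditional proportion with a first event in each interval.

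Crude incidence is also planned: "The number of participants who experienced TEAEs of special interest listed below will be summarized by maximum severity" (Table 3.2.26). Neither document mentions cumulative incidence or competing risks, or says how the onset curves should be read.

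**The concern.** Treatment ends for progression, death, unacceptable toxicity or withdrawal of consent (SAP 3). Once 30 days have passed since the last dose, or the participant has died, a first treatment-emergent colitis can no longer occur by definition. The onset analysis nevertheless groups these participants with those still on drug at the cutoff. For the latter, censoring is administrative and harmless. For the former, Kaplan-Meier carries on as if they would later have the event at the rate seen in those still on treatment.

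For the neutrophil plot the argument is about follow-up rather than the event definition. Protocol Table 7 schedules hematology during treatment, at end of treatment and at the safety follow-up visit 30 to 35 days later, so graded values also end soon after stopping.

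What is at stake is a safety display for class toxicities that the two maintenance regimens were meant to reduce (Protocol 1.4). A reader who takes the height of a curve at 12 or 24 months as the proportion of patients affected will read too high a number, and one that can disagree with the crude table in the same report.

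**Working it through.** The documents give no figure for time to onset of these events, so there is nothing to reproduce first. The check has two parts.

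**Direction.** At each event time the Aalen-Johansen estimate adds S(t-) × d/Y. Here d is the number of first events, Y is the number at risk, and S is the probability of being free of both the event and any competing exit. 1-KM adds K(t-) × d/Y, where K is reduced by the event alone. Since S ≤ K at every time, 1-KM is never below the cumulative incidence, and it exceeds it as soon as one event follows a competing exit. This needs no assumption about hazards.

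**Size.** This does need assumptions.

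- Stop time: Protocol Synopsis, about 52 weeks on treatment, taken as 364 days. I treat it as exponential, with 364 days as either the median (c = ln 2/364 = 0.00190 per day) or the mean (c = 1/364 = 0.00275 per day).
- Horizon: 24 months, taken as 728 days (Protocol 4.5, at least 24 months of participation).
- True 24-month share: 35%, the any-grade diarrhea/colitis frequency in Study INCB 50465-101 (Protocol 1.3). Also 10%, because the same section reports no Grade 3 or higher nonhematological treatment-related event in 10% or more of subjects. Using either as a 24-month share is an assumption.
- Window: G(t) = 1 for t < 30 days, then exp(-c(t - 30)), so the 30 days after the last dose are counted.
- Event hazard h: either constant over 728 days, or constant over the first 182 days and zero afterwards.

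With H(t) the cumulative event hazard,

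- share affected = ∫ h(t) exp(-H(t)) G(t) dt from 0 to 728;
- 1-KM = 1 - exp(-H(728)).

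I solved h so that the share equals 35% or 10%, then read off 1-KM:

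| Onset pattern | Stop time | True share | h per day | 1-KM at 24 months |
|---|---|---|---|---|
| Constant | median 364 d | 35% | 0.00113 | 1 - exp(-0.00113 × 728) = 56% |
| Constant | mean 364 d | 35% | 0.00142 | 64% |
| First 6 months | median 364 d | 35% | 0.00270 | 1 - exp(-0.00270 × 182) = 39% |
| First 6 months | mean 364 d | 35% | 0.00285 | 41% |
| Constant | median 364 d | 10% | 0.000258 | 17% |
| Constant | mean 364 d | 10% | 0.000317 | 21% |
| First 6 months | median 364 d | 10% | 0.000653 | 11% |
| First 6 months | mean 364 d | 10% | 0.000686 | 12% |

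**Simulation.** In 1,000 trials of 120 participants (constant hazard, median stop 364 days, true 24-month share 20%), the mean 1-KM was 33.4% and the mean Aalen-Johansen estimate 19.9%. The crude proportion over all follow-up was 21.3%. The crude table is therefore close to the truth; the curve is not.

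**The case against.** The best case for the plan has four parts.

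1. The share of patients affected is already given directly by the crude counts. A reader might infer that the trial's adverse event frequencies as a whole will be overstated. They will not be: Table 3.2.26 and the other crude summaries are sound. This stands.

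2. For onset, the SAP plans plots only, with no Kaplan-Meier rate at a timepoint, no median and no confidence interval. Where it wants rates at timepoints, as for resolution in 9.2.2, it says so. The misreading is therefore a risk, not something the plan commits to. This stands in part: a plotted curve with no caveat invites that reading.

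3. The scope is narrow. A reader might extend the point to every event of special interest, to ALT and AST, or to survival columns in the life tables. The Kaplan-Meier plots cover only rash, colitis, diarrhea and neutrophils. The SAP text defines only interval conditional proportions for the life tables, and these are legitimate on-treatment rates. This stands.

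4. Onset risk while on treatment is a valid descriptive quantity. Reading 1-KM as the risk if nobody stopped, however, requires stopping to be unrelated to the event hazard. That is doubtful when the stop is for another class toxicity. In Study INCB 50465-101 "Twelve (19%) of the 63 subjects discontinued study treatment due to the following AEs", a list that includes pneumonitis and exfoliative dermatitis. In fairness, 4 of those 12 stops were for diarrhea, colitis or cytomegalovirus colitis, which would be events on some of these curves rather than competing exits.

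**Conclusion.** The point holds for the five adverse event onset plots and the neutrophil plot. Read as the share of patients affected, 1-KM is biased upward, whatever the hazards.

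The size is not settled by the documents. For a true 24-month share of 35% the curve would show about 39-41% to 56-64%; for 10%, about 11-12% to 17-21%. The lower figures assume onset only in the first 6 months, the upper ones a constant hazard for 24 months. Neither pattern is established: both regimens change after 8 weeks, while Protocol 5.4.1.4 says most immune-related events come after the first 9 weeks. The 52 weeks also covers all reasons for stopping, including the event itself, so using it for competing stops alone tends to enlarge the gap.

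A reader might compute 68% against 35% by ignoring the 30 days after the last dose. The SAP's own window rules that out as the figure to quote. For the Grade 3 or higher plots, the 10% rows are the closer guide.

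These are descriptive displays. No futility rule, group comparison or primary result depends on them, so this is a cheap improvement rather than a threat to the trial's conclusions.

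**What to change.** For Figure 4.5.1 and Figure 4.6.2, present Aalen-Johansen cumulative incidence. Count death and permanent discontinuation without the event as competing events, and censor only participants still at risk at the cutoff or lost to follow-up. For treatment-emergent events, date the discontinuation at last dose plus 30 days. For neutrophils, where 9.3.4 has no such window, the SAP should state the date used.

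Keep the life-table interval proportions and describe them as on-treatment rates. If a Kaplan-Meier curve is retained, label it as conditional on remaining on treatment.

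The cost is a few lines of SAP text and a little extra programming. Onset, last-dose, discontinuation and death dates are already collected. What is lost is a picture of the hypothetical risk if nobody stopped, which the cumulative-incidence curve does not show.

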
 Diarrhea (Grade 2). 	
Step 1: Interrupt INCB050465. Perform work-up for infection (including CMV, C. difficile, etc) immediately. Initiate or continue supportive care (see Section 5.4.1.2). Monitor approximately every 48 hours until resolution.
 
Step 2: If improved within 48 hours and/or infection* is confirmed, restart INCB050465 at the same schedule and dose after resolved to ≤ Grade 1 and continue to monitor.
 
*For infectious diarrhea/colitis, follow institutional standard-of-care guidelines and restart INCB050465 according to clinical judgement after resolved to ≤ Grade 1. Consult with medical monitor if needed.
 
Step 3: If not improved within 48 hours and infection is ruled out, start oral steroids, or consider IV steroids if participant is being given IV fluids. If no improvement with oral steroids, switch to IV steroids.
 
Step 4: When diarrhea resolves to ≤ Grade 1, continue supportive care and taper steroids according to institutional standard of care. When taper is complete (eg, no steroid or ≤ 10 mg/day prednisone or equivalent) and diarrhea is ≤ Grade 1, restart INCB050465 at the next lower dose with approval of the medical monitor (see Table 4 for dose levels).
 
Step 5: If Grade 2 diarrhea reoccurs, treat per guidance for diarrhea (≥ Grade 3)/noninfectious colitis.
 
Step 6: If ≥ Grade 2 diarrhea reoccurs a third time, permanently discontinue INCB050465.
								

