The longest duration of a TEAE of any grade is defined as the longest interval between the date of occurrence of a TEAE and the date of resolution. The longest duration of a Grade 3 or higher TEAE is defined as the longest interval between the date of occurrence of a Grade 3 or higher TEAE and the date of improvement to Grade 2 or lower. If participants have missing or partial onset/end date of a TEAE, the partial or missing dates will be handled using the rules explained in Section 4.1.4. Participants who have missing end date of a TEAE at the time of analysis will be right-censored using the following algorithm:

- If the TEAE is serious, then the participant will be censored at the earlier date of data cutoff, study discontinuation, and death.
- If the TEAE is not serious,
  - If the participant is ongoing with study treatment, then the participant will be censored at the data cutoff date, OR
  - If the participant discontinued treatment, then the participant will be censored at date of safety follow-up visit, or 35 days after the end of treatment visit (or after the last dose if the end of treatment visit was not performed), whichever is later; the censored date will be truncated by the earlier date of data cutoff, study discontinuation, and death if beyond.

Longest duration of new or worsening Grade 3 or higher colitis, diarrhea, rash, and febrile neutropenia will be summarized. In addition, longest duration of new or worsening AEs of any grade will be summarized for colitis, diarrhea, and rash.

The total number of participants whose TEAE of any grade resolved or whose Grade 3 or higher TEAE improved to Grade 2 or lower and the number of participants censored will be summarized. The Kaplan-Meier estimate of median time to resolution/improvement and its 95% CIs will be provided, with the CIs calculated using the generalization of Brookmeyer and Crowley's method (1982) with log-log transformation (Klein and Moeschberger 1997). Resolution/improvement rates at selected timepoints will also be provided with 95% CIs calculated using Greenwood's formula to estimate the standard error.

TEAEs of special interest to be summarized may be adjusted based on emerging data.

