- Section 9.2.2 was updated to include details of analyses on time to onset of selected TEAEs of special interest. Summaries of longest duration of selected TEAEs of special interest were added to have a better understanding of the safety profile in terms of duration of class-effect AEs as well as AEs influenced by treatment regimens. "Grade 2 or higher" was changed to "Grade 3 or higher" for time to onset summary of rash. This change was made to be consistent with other PI3K inhibitors, which highlighted more severe cutaneous reactions graded as Grade 3 or higher in the labeling. "Herpes simplex virus infection" was changed to "herpes simplex" based on the MedDRA coding dictionary as a broader term. Exfoliative dermatitis was added to the list of TEAEs of special interest.

- Section 9.2.3 was updated to include summary of TEAEs by PT and maximum severity in decreasing order of frequency, summary of longest duration of selected TEAEs of special interest, and additional supporting summaries during the INCB050465 initial QD dosing period and the maintenance dosing period, which will provide supportive data of the safety profile of the maintenance dose. Summary of nonserious TEAEs by SOC and PT was removed because it will not be used for the clinical study report but will be provided for result disclosure.
- Section 9.3.2 was modified to include ALT and AST in the line graphs as additional supportive analyses for laboratory events of special interest.
- Section 9.3.3 was added to identify potential Hy's law events to better monitor liver toxicity.
- Section 9.3.4 was updated to align with the analysis plan for adverse events of special interest. Summary of worsening of laboratory events of special interest was removed because this is covered by the summary of worsening of laboratory abnormalities.
- Section 9.5 was updated to change the high threshold of QTcF and QTcB interval from 460 to 450 milliseconds for purpose of analysis. This change is to comply with the categories outlined in FDA Guidance for Industry (E14 Clinical Evaluation of QT/QTc Interval Prolongation and Proarrhythmic Potential for Non-Antiarrhythmic Drugs) used to characterize outliers in OTc values.

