3.2.19	Summary of Treatment-Emergent Adverse Events Leading to INCB050465 Dose Interruption by MedDRA System Organ Class and Preferred Term	Safety	X
3.2.20	Summary of Treatment-Emergent Adverse Events Leading to Discontinuation of INCB050465 by MedDRA System Organ Class and Preferred Term	Safety	X
3.2.25	Summary of Treatment-Emergent Adverse Events by MedDRA Preferred Term and Maximum Severity in Decreasing Order of Frequency	Safety	
3.2.26	Summary of Selected Treatment-Emergent Adverse Events of Special Interest by Maximum Severity	Safety	
3.2.27	Summary of Time to Onset of Selected Treatment-Emergent Adverse Events of Special Interest	Safety	
3.2.28	Summary of Time to Onset of Selected Treatment-Emergent Adverse Events of Special Interest: Life-Table Method	Safety	
3.2.29	Summary of Longest Duration of Selected Treatment-Emergent Adverse Events of Special Interest	Safety	
3.3.1.1	Summary of Laboratory Values - Hematology	Safety	X
3.3.1.2	Summary of Laboratory Values - Chemistry	Safety	X
3.3.3.1	Shift Summary of Hematology Laboratory Values in CTC Grade - To the Worst Abnormal Value	Safety	X
3.3.3.2	Shift Summary of Chemistry Laboratory Values in CTC Grade - To the Worst Abnormal Value	Safety	X
3.3.3.4	Treatment-Emergent Worsening of Laboratory Abnormalities - Hematology	Safety	X
3.3.3.5	Treatment-Emergent Worsening of Laboratory Abnormalities - Chemistry	Safety	X
3.3.6	Time to Onset of Treatment-Emergent Worsening of Laboratory Events of Special Interest	Safety	
3.3.7	Time to Onset of Treatment-Emergent Worsening of Laboratory Events of Special Interest: Life-Table Method	Safety	
3.4.1	Summary of Systolic Blood Pressure	Safety	X
3.4.2	Summary of Diastolic Blood Pressure	Safety	X
3.4.3	Summary of Pulse	Safety	X
3.4.4	Summary of Respiratory Rate	Safety	X
3.4.5	Summary of Body Temperature	Safety	X
3.4.6	Summary of Weight	Safety	X

Table No.	Title	Population	Standard
3.5.1	Summary of PR Interval (ms) From 12-Lead ECG	Safety	X
3.5.2	Summary of QRS Interval (ms) From 12-Lead ECG	Safety	X
3.5.3	Summary of QT Interval (ms) From 12-Lead ECG	Safety	X
3.5.4	Summary of QTcB Interval (ms) From 12-Lead ECG	Safety	X
3.5.5	Summary of QTcF Interval (ms) From 12-Lead ECG	Safety	X
3.5.6	Summary of RR Interval (ms) From 12-Lead ECG	Safety	X
3.5.8	Summary of Outliers of QT, QTcB, and QTcF Interval Values From 12-Lead ECG	Safety	X
3.5.9	Summary of Clinically Significant ECG Abnormality	Safety	X

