# Figures

Figure No.	Title	
4.1.1	Forest Plot of Objective Response Rate as Determined by Independent Review Committee	
4.2.1	Kaplan-Meier Estimates of Duration of Response as Determined by Independent Review Committee	
4.2.2	Kaplan-Meier Estimates of Duration of Response as Reported by Investigator	
4.2.3	Kaplan-Meier Estimates of Progression-Free Survival as Determined by Independent Review Committee	
4.2.4	Kaplan-Meier Estimates of Progression-Free Survival as Reported by Investigator	
4.2.5	Kaplan-Meier Estimates of Overall Survival	
4.2.6	Waterfall Plot of Best Percent Change in Sum of Target Lesions as Determined by Independent Review Committee	
4.2.7	Waterfall Plot of Best Percent Change in Sum of Target Lesions as Reported by Investigator	
4.3.1	Kaplan-Meier Estimates of Duration of Response as Determined by Independent Review Committee – Censoring Crossover Participants	
4.3.2	Kaplan-Meier Estimates of Duration of Response as Reported by Investigator – Censoring Crossover Participants	
4.3.3	Kaplan-Meier Estimates of Progression-Free Survival as Determined by Independent Review Committee – Censoring Crossover Participants	
4.3.4	Kaplan-Meier Estimates of Progression-Free Survival as Reported by Investigator – Censoring Crossover Participants	
4.5.1	Kaplan-Meier Estimates of Time to Onset of Selected TEAEs of Special Interest	
4.5.2	Kaplan-Meier Estimates of Longest Duration of Selected TEAEs of Special Interest	
4.6.1	Line Graph of Mean Values Over Time for Selected Laboratory Values (Hemoglobin, Platelet Counts, Leukocytes, Neutrophils, and Lymphocytes)	
4.6.2	Kaplan-Meier Estimates of Time to Onset of Selected Worsening Laboratory Events of Special Interest	

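### The Kaplan-Meier duration analysis of selected adverse events of special interest uses each participant's longest interval, so with varying durations and repeat episodes it exceeds a typical episode and rises with time on treatment

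*SAP*

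**What the plan says.** SAP 9.2.2 defines duration only through the participant's maximum. For any grade: "The longest duration of a TEAE of any grade is defined as the longest interval between the date of occurrence of a TEAE" and its resolution. For severe events: "The longest duration of a Grade 3 or higher TEAE is defined as the longest interval between the date of occurrence of a Grade 3"; the sentence goes on to take in higher grades and ends the interval at improvement to Grade 2 or lower. The any-grade version covers diarrhea, colitis and rash. The Grade 3 or higher version covers those three and febrile neutropenia. The SAP allows the list to be adjusted later.

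The estimator follows in the same section: "The Kaplan-Meier estimate of median time to resolution/improvement and its 95% CIs will be provided". Resolution or improvement rates at selected timepoints are added. The planned outputs confirm the basis: Table 3.2.29 is "Summary of Longest Duration of Selected Treatment-Emergent Adverse Events of Special Interest" and Figure 4.5.2 is "Kaplan-Meier Estimates of Longest Duration of Selected TEAEs of Special Interest". The SAP plans no duration analysis of first episodes or of all episodes.

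SAP 11.2 (Amendment 1) says the summaries were added to understand the safety profile "in terms of duration of class-effect AEs as well as AEs influenced by treatment regimens".

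Three Protocol provisions bear on this. Section 6.3 sets no fixed end of treatment. Table 5 provides for recurrence, including the case where Grade 2 or higher "diarrhea reoccurs a third time"; that step ends treatment, as does recurrence under the Grade 3 or higher diarrhea and colitis row. Section 8.1.2 records every change in severity as a separate adverse event.

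**The concern.** A median time to resolution is normally read as how long an episode lasts once it starts. A median taken over each participant's longest interval answers another question: how long was the worst episode so far? The two agree only if participants have one episode each or if all episodes last equally long. Otherwise the maximum sits above a typical episode. It also climbs as participants stay on drug and collect episodes, without any change in how quickly an episode resolves.

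At stake is the purpose stated in SAP 11.2. A figure that mixes episode length with episode count and exposure does not describe the duration of a class-effect event. Someone using it to judge how long colitis or diarrhea usually lasts would expect too long a course. The onset analysis in the same section counts to the first occurrence, so the two analyses can describe different episodes in the same participant.

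**Working it through.** **Inputs from the documents.** The definitions, the estimator and the output titles (SAP 9.2.2 and Appendix A), open-ended treatment (Protocol 6.3) and the recurrence rules (Protocol Table 5). The plan states no duration, recurrence rate or episode distribution, so there is no figure of its own to reproduce. All rates and distributions below are assumptions.

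**Step 1: a fixed number of episodes.** For K independent episodes with distribution F, the median of the longest is F⁻¹(0.5^(1/K)).

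- Exponential, as a ratio to the single-episode median: −ln(1 − 0.5^(1/K)) / ln 2. For K = 2: −ln(1 − 0.7071)/0.6931 = 1.228/0.6931 = 1.77. For K = 3: −ln(1 − 0.7937)/0.6931 = 1.578/0.6931 = 2.28.
- Lognormal, sigma 0.5: exp(0.5 × z), where z is the normal quantile at 0.5^(1/K). For K = 2: exp(0.5 × 0.545) = 1.31. For K = 3: exp(0.5 × 0.819) = 1.51.
- Constant duration, or K = 1: ratio 1.00.

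**Step 2: a mix of participants.** If those with the event have 1, 2 or 3 exponential episodes in 60/30/10% of cases, solving 0.6F + 0.3F² + 0.1F³ = 0.5 gives F = 0.610 and a ratio of 1.36. At 80/15/5% the ratio is 1.17.

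**Step 3: dependence on exposure.** With a Poisson number of episodes of mean μ = rate × time, given at least one, P(longest ≤ x) = [exp(−μ(1 − F(x))) − exp(−μ)] / [1 − exp(−μ)]. Setting this to 0.5 at μ = 1 (one per year, one year): F = 1 + ln(0.5 × 0.6321 + 0.3679) = 0.620, and the exponential ratio is −ln(0.380)/0.6931 = 1.40.

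As a rough model of the diarrhea and colitis discontinuation rules, cap the count at two. The weights become 0.3679/0.6321 = 0.582 for one episode and 0.418 for two. Solving 0.582F + 0.418F² = 0.5 gives F = 0.600 and a ratio of 1.32.

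| One episode per year | 8 weeks | 6 months | 1 year | 2 years |
|---|---|---|---|---|
| Exponential, no cap | 1.06 | 1.19 | 1.40 | 1.82 |
| Exponential, at most 2 | 1.05 | 1.17 | 1.32 | 1.54 |
| Lognormal (sigma 0.5), no cap | 1.02 | 1.08 | 1.17 | 1.33 |

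With the cap of two, the exponential ratio cannot exceed 1.77.

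**Step 4: the Kaplan-Meier estimate itself.** This was simulated with censoring at the end of follow-up, one episode per year and exponential episodes of mean 14 days (true median 14 × ln 2 = 9.7 days).

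| Follow-up, days | 56 | 182 | 365 | 730 |
|---|---|---|---|---|
| Median, longest episode (days) | 10.0 | 11.6 | 13.5 | 17.5 |
| Median, first episode (days) | 9.5 | 9.8 | 9.7 | 9.6 |

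Censoring does not remove the effect, and the first-episode median does not drift. When every episode was set to exactly 14 days, both medians were 14.0 at every follow-up length.

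**The case against.** **The maximum is declared.** Both definitions and both output titles say longest, and the worst episode is a legitimate descriptive safety quantity. That stands. The fault is that the Kaplan-Meier sentence drops the word and that no typical-episode analysis sits beside it.

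**Repeats are limited.** Table 5 ends treatment at the third occurrence of Grade 2 or higher diarrhea, and at recurrence under the Grade 3 or higher diarrhea and colitis row. This stands and lowers the size, as the capped row shows. It does not remove the effect: two episodes remain possible, and neither Grade 1 diarrhea nor rash falls under these stopping rules.

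**Fragmented records pull the other way.** Because each severity change is a separate record, the longest any-grade interval may be only part of an episode. This stands. The SAP has no joining rule, so the net direction in the any-grade analysis is not certain. It also constrains the remedy: a first-episode analysis without such a rule could pick up an initial low-grade fragment.

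**Stronger readings the documents do not support.** A reader might infer that the median grows with exposure even when all episodes are of equal length. It does not; durations must vary. A reader might infer that one regimen will look slower to resolve than the other. Results are shown by regimen, but SAP 3.2 and 5.2 rule out statistical comparison, and nothing establishes how exposure will differ. A reader might also see a second bias in censoring unresolved non-serious events at the data cutoff for participants still on treatment, since the onset analysis has participants without the event "right-censored at the earlier of 30 days after the last dose date and date of last study visit". But cutoff censoring of ongoing events is conventional. Protocol Table 5 also asks for checks about every 48 hours for diarrhea and noninfectious colitis, and Table 3 for at least weekly neutrophil counts after febrile neutropenia. For most covered events, resolution is therefore not learned only at 12-weekly visits.

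**Conclusion.** The point holds within limits. For four event terms, not for all events of special interest, the Kaplan-Meier median and rates describe the longest interval, not a typical episode. If durations vary and some participants have repeat episodes, the median is above the typical duration and rises with time on treatment, although the underlying distribution is unchanged. The illustrations at one year and one episode per year run from 1.17 times (lognormal, sigma 0.5) to 1.40 times (exponential), with 1.32 for the capped exponential case. They assume independent, identically distributed, fully joined episodes. If recurrence is rare the effect is close to nil.

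No hypothesis, stopping rule or planned comparison uses this output. It is a cheap improvement to a secondary safety analysis.

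**What to change.** In SAP 9.2.2, with matching changes to Table 3.2.29 and Figure 4.5.2:

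1. For the any-grade analysis, define an episode by joining consecutive severity-change records of the same event.
2. Run the Kaplan-Meier time to resolution or improvement on each participant's first episode, or on all episodes with variance clustered by participant.
3. Report the number of episodes per participant.
4. Keep the longest duration as a descriptive worst-case summary, labelled *longest episode* wherever it appears, including the text. State which interval counts when one has resolved and another is ongoing.
5. Leave the cutoff-censoring rule unchanged.

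The cost is SAP wording and a modest re-derivation from adverse event dates already collected. The first-episode curve does not show the worst case; the retained longest-episode summary does.
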